8.4 Reporting Procedures

8.4.1 Serious Adverse Event Reporting

When an Investigator determines that an AE meets the protocol definition of an SAE during the study, he/she must notify the Sponsor using an SAE Report Form **within 24 hours of the study site personnel's knowledge of the event**, regardless of the Investigator assessment of the relationship of the event to study drug. Relevant information will be entered on the AE page and on all other applicable pages of the CRF; source documentation should not be sent with the SAE Report Form unless requested.

Follow-up information received on SAEs should be emailed or faxed to the Sponsor within 1 business day of receipt (refer to [Medical Monitor/ Sponsor Information Page](#) for contact information). This information should be included on a follow-up SAE form and filed with the original SAE information.

All SAEs will be followed until resolution, until the condition stabilizes, until the event is otherwise explained, or until the subject is lost to follow-up.

The completed SAE Report form should be submitted via email or fax to the SAE Reporting Contact which can be found on the [Medical Monitor/ Sponsor Information Page](#) of this protocol.

Do not delay reporting a suspected SAE in order to obtain additional information. Any additional information, if collected, can be reported as a follow-up to the initial report.

8.4.2 Regulatory Reporting Requirements for Serious Adverse Events

Prompt notification by the Investigator to the Sponsor of SAEs (even for non-interventional post-marketing studies) is essential so that legal obligations and ethical responsibilities towards the safety of subjects and the safety of a product under clinical investigation are met.

The Sponsor has a legal responsibility to notify both the local regulatory authority and other regulatory agencies about the safety of a product under clinical investigation. The Sponsor will comply with country-specific regulatory requirements relating to safety reporting to the regulatory authority, IRB/IEC, and Investigators.

Investigator safety reports are prepared for suspected unexpected serious adverse reactions according to local regulatory requirements and are forwarded to Investigators as necessary.

An Investigator who receives an Investigator safety report describing a SAE(s) or other specific safety information (e.g., summary or listing of SAEs) from the Sponsor will file it with the Investigator's Brochure and will notify the IRB/IEC, if appropriate, according to local requirements.

8.5 Pregnancy Management and Reporting

Any female subject who becomes pregnant during the study will be withdrawn. Details will be collected for all pregnancies in female subjects and female partners of male subjects that begin after the start of dosing and through the Follow-up visit. Pregnancy is not automatically considered an AE.

If a pregnancy is reported, then the Investigator should complete a Pregnancy Report Form and submit via email or fax to the Pregnancy Reporting Contact for which contact information can be found on the [Medical Monitor / Sponsor Information Page](#) of this protocol, within 2 weeks of learning of the pregnancy. The subject will also be followed to determine the outcome of the pregnancy. Information on the status of the mother and child will be forwarded to the Sponsor. Generally, follow-up will be no longer than 6 to 8 weeks following the estimated delivery date. Any premature termination of the pregnancy will be reported.

Any SAE occurring in association with a pregnancy brought to the Investigator's attention after the subject has completed the study and considered by the Investigator as possibly related to the study drug must be promptly reported to the Sponsor or the Sponsor's representative.

The Investigator must attempt to collect pregnancy information on any female partners of male study subjects who become pregnant while the subject is enrolled in the study. Pregnancy information must be reported to the Sponsor or the Sponsor's representative as described above. The partner will also be followed to determine the outcome of the pregnancy. Information on the status of the mother and child will be forwarded to Sponsor or the Sponsor's representative. Generally, follow-up will be no longer than 6 to 8 weeks following the estimated delivery date. Any premature termination of the pregnancy will be reported on the Pregnancy Report Form.

9 Data Management

For this study, subject data will be entered into the Sponsor-defined CRFs, transmitted electronically to the Sponsor or designee, and combined with data provided from other sources in a validated data system.

Management of clinical data will be performed in accordance with applicable Sponsor standards and data cleaning procedures will be used to ensure the integrity of the data, e.g., errors will be corrected, and inconsistencies queried in the data.

Adverse events and relevant medical history will be coded using the most current version of the Medical Dictionary for Regulatory Activities. Concomitant medications will be coded with the most current version of World Health Organization Drug Global Dictionary.

The Investigator will retain original source documents and the Sponsor will receive CRF-required data as electronic datasets. Subject initials will not be collected or transmitted to the Sponsor.

10 Statistical Considerations and Data Analyses

This study will evaluate the efficacy and safety of tapinarof cream, 1% compared with vehicle control cream in adults and children with AD.

10.1 General Considerations

All study data will be summarized by treatment group using descriptive statistics. Categorical variables will be reported using frequency and percentage (e.g., gender, race). Continuous variables will be reported using number of subjects, mean, standard deviation (SD), median, minimum, and maximum. All efficacy and safety data will be listed by subject.

10.2 Determination of Sample Size

It is estimated that the proportion of subjects who will achieve a vIGA-AD™ score of 0 or 1 and at least a 2-grade reduction from Baseline at Week 8 will be 45% for subjects receiving tapinarof compared with 25% for subjects receiving vehicle control, based upon the Phase 2 results. With 400 subjects randomized in a 2:1 ratio (267 subjects receiving tapinarof, and 133 subjects receiving vehicle control), this will provide 97.2% power for statistical significance (2-sided $p < 0.05$). The power is calculated from a Fisher Exact sample size calculation. It is assumed that 15% of the subjects receiving tapinarof will be lost to follow-up by 8 weeks compared with 30% of the subjects receiving vehicle control. These subjects will be included in the primary analysis using the multiple imputation method.

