5. DETERMINATION OF SAMPLE SIZE

It is estimated that the proportion of subjects who will achieve a vIGA-ADTM score of 0 or 1 and at least a 2-grade reduction from Baseline to Week 8 will be 45% for subjects receiving tapinarof compared with 25% for subjects receiving vehicle control, based upon the Phase 2 results. With 400 subjects randomized in a 2:1 ratio (267 subjects receiving tapinarof, and 133 subjects receiving vehicle control), this will provide 97.2% power for statistical significance (2-sided p <0.05). The power is calculated from a Fisher Exact sample size calculation. It is assumed that 15% of the subjects receiving tapinarof will be lost to follow-up by 8 weeks compared with 30% of the subjects receiving vehicle control. These subjects will be included in the primary analysis using the multiple imputation method.

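### The stated 97.2% power takes all 400 Week 8 outcomes as observed; with the 15% and 30% loss assumed in the same paragraph it is about 92%.

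*Protocol*

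**What the plan says.** Protocol 10.2 gives the design response rates ("will be 45% for subjects receiving tapinarof compared with 25% for subjects receiving vehicle control, based upon the Phase 2 results") and the power: "With 400 subjects randomized in a 2:1 ratio (267 subjects receiving tapinarof, and 133 subjects receiving vehicle control), this will provide 97.2% power". The level is two-sided 0.05, and the method is named: "The power is calculated from a Fisher Exact sample size calculation".

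The paragraph then turns to attrition, with the higher rate applying to the vehicle arm: "It is assumed that 15% of the subjects receiving tapinarof will be lost to follow-up by 8 weeks compared with 30% of the subjects". It closes with the handling: "These subjects will be included in the primary analysis using the multiple imputation method".

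SAP Section 5 repeats the text, including "this will provide 97.2% power for statistical significance". Neither document inflates the sample size for the assumed loss, reduces the power for it, or labels 97.2% as a complete-data figure.

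Protocol 10.6 and SAP 10.4 set out the imputation: 100 imputed data sets from a model using earlier post-baseline visits, baseline strata and treatment. SAP 11.1 pools the log relative risk over the imputations with PROC MIANALYZE.

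**The concern.** The power and the attrition assumption stand side by side, so a reader will take it that the first allows for the second. If 97.2% was computed at 267 vs 133, the lost subjects were counted as if their Week 8 outcomes were known.

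Imputing an outcome does not supply the missing information. Rubin's rules add the between-imputation variance to the standard error, and the pooled test uses that larger standard error. Unless earlier visits predict Week 8 very well, the test has close to the precision of the observed subjects alone. The loss also falls hardest on the smaller arm: vehicle goes from 133 to about 93.

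What is at stake is the stated risk of a false negative under the design effect. A figure of 97.2% implies a 2.8% risk.

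**Working it through.** **Inputs (Protocol 10.2).** Response 45% vs 25%; 267 vs 133 randomized; two-sided alpha 0.05; Fisher exact test; loss 15% and 30%.

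**Observed subjects after the assumed loss.**
- Tapinarof: 267 × 0.15 ≈ 40 lost, leaving about 227.
- Vehicle: 133 × 0.30 ≈ 40 lost, leaving about 93.

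**Fisher power.** For every pair (x1, x2), weight by Binomial(x1; n1, 0.45) × Binomial(x2; n2, 0.25), and add the weights where Fisher's test rejects. The two-sided test was taken in two common forms: 0.025 in each tail, and the two-sided p-value that sums all tables no more likely than the one observed.

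**Normal check.** Power = Φ[(0.20 − c − 1.96 × SE0)/SE1]. SE0 uses the pooled proportion and SE1 the separate proportions. The continuity correction c is 0 or ½(1/n1 + 1/n2).
- 267/133: pooled proportion 0.3835, SE0 = 0.0516, SE1 = 0.0483. With c = 0: Φ(2.045) = 98.0%. With c = 0.0056: Φ(1.928) = 97.3%.
- 227/93: pooled proportion 0.3919, SE0 = 0.0601, SE1 = 0.0557. With c = 0: Φ(1.475) = 93.0%. With c = 0.0076: Φ(1.339) = 91.0%.

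| Method | 267 / 133 | 227 / 93 |
|---|---|---|
| Fisher, 0.025 per tail | 97.3% | 91.2% |
| Fisher, minimum-likelihood two-sided p | 97.6% | 92.1% |
| Normal, continuity-corrected | 97.3% | 91.0% |
| Normal, pooled | 98.0% | 93.0% |
| Normal, unpooled | 98.5% | 94.8% |

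The plan's 97.2% is reproduced, to within rounding of method, only in the first column. No method in the second column comes within 2 points of it.

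**Multiple imputation.** The pooled variance is T = W + (1 + 1/M)B, where W is the mean within-imputation variance, B the between-imputation variance and M = 100. The pooled log relative risk test was simulated (4,000 trials, unstratified, data missing at random). Earlier-visit information was a binary status. Its correlation with Week 8, and the share of dropouts who have it, are assumptions, because the documents give neither.

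| Correlation with Week 8 | Share of dropouts with the earlier visit | Power | Information missing |
|---|---|---|---|
| none used | – | 91.9% | 27% |
| 0.3 | 50% | 91.4% | 26% |
| 0.3 | 100% | 91.9% | 25% |
| 0.5 | 50% | 92.4% | 25% |
| 0.5 | 100% | 93.1% | 22% |
| 0.7 | 50% | 92.9% | 22% |
| 0.7 | 100% | 94.2% | 17% |

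For reference, the same log relative risk test without imputation has 97.5% power at 267/133 and 91.2% at 227/93. Simulations stratified as planned, with a Mantel-Haenszel relative risk, gave 91.1% when imputing by arm only. They gave 93.2% to 93.5% with assumed earlier-visit correlations of 0.45 to 0.70, or half of that. No setting returned to 97%.

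**The case against.** The strongest reply is that not every early loss is a missing outcome. The primary estimand is composite: discontinuation for an adverse event or lack of efficacy, or use of a specified prohibited medication, is scored as failure (Protocol 10.4.2.1, SAP 10.4 and 11.1), and such subjects have a known outcome. An Early Termination assessment on Day 43 or later can also be windowed to Week 8 (SAP Section 7). If part of the 15% and 30% is of this kind, less information is lost. Fisher power (minimum-likelihood form) would then be:

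| Share of losses scored as failure | 45%/25% among all with a known outcome | 45%/25% as completer rates |
|---|---|---|
| one quarter (237 / 103 known) | 93.8% | 95.6% |
| one half (247 / 113) | 95.7% | 97.6% |
| three quarters (257 / 123) | 96.6% | 98.7% |

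With every loss a failure and 45%/25% as completer rates (0.45 × 0.85 = 38.25% vs 0.25 × 0.70 = 17.5%), power is about 99%.

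The arithmetic is right, and it shows that about 92% rests on how the loss is read. It does not rescue the stated figure. Protocol 10.2 describes these subjects as lost to follow-up and sends them to multiple imputation, not to failure scoring. Scoring all missing data as failure is a sensitivity analysis (Protocol 10.6, SAP 10.4). The documents give no share of losses expected to be composite failures, and the 97.2% is reproduced by the plain complete-data calculation.

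Two further points stand. Nothing was miscalculated for the inputs used; the error is in what the figure is said to represent. And no power target is missed, since the documents set none.

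**Conclusion.** The concern holds. The 97.2% is the power with complete Week 8 data. Under the loss assumed in the same paragraph it is about 92% on the plan's own Fisher basis (91.2% to 92.1%), and about 91% to 94% for the pooled relative risk analysis by simulation. The Fisher figures put the risk of missing a true 45% vs 25% effect at 7.9% to 8.8%, about three times the implied 2.8%.

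This rests on three assumptions: all of the 15% and 30% lack Week 8 data, as the paragraph reads; data are missing at random; and 45% and 25% apply whether or not a subject drops out. The upper part of the simulated range also depends on assumed visit correlations.

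The practical weight is moderate. Power stays above 90% on these calculations, and no test or decision rule changes. The logit-based stratified estimate named in SAP 11.1 may have lower power with eight sparse strata. That depends on strata sizes and zero-cell handling the documents do not give, so it is a separate matter and is not relied on here.

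**What to change.** In Protocol 10.2 and SAP Section 5:

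- Label 97.2% as the power with no missing Week 8 data.
- Add the power under the 15% and 30% loss: either about 92% (Fisher exact, 227 vs 93 observed), or a simulated figure for the planned multiple-imputation relative risk analysis, with the assumed visit correlations and the missing-at-random assumption stated.
- If the sponsor expects part of the loss to be composite failures, state that share and whether 45% and 25% already include those failures, and compute the power on that basis.

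The cost is wording only. The sample size stays at 400 and no analysis changes; the quoted power becomes less favourable by about 5 points (97.2% − 92.1% = 5.1).

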10.3 Analysis Populations

10.3.1 Safety

All randomized subjects who receive at least 1 application of study drug will be included in the Safety population. Subjects will be analyzed as treated.

10.3.2 Intent-To-Treat

All randomized subjects will be included in the Intent-to-treat (ITT) population. Subjects will be analyzed as randomized.

10.3.3 Per-Protocol

All subjects in the ITT population who did not have any major protocol deviations or other events that may impact the interpretation of the primary efficacy endpoint will be included in the Per Protocol (PP) population.

10.3.4 Pharmacokinetic

All subjects who undergo plasma PK sampling and have evaluable concentration-time data for analysis will be included in the PK population. A sample that is below the quantification limit of the assay is considered evaluable.

10.4 Planned Analyses

All efficacy and safety measures over the course of the study will be presented. Details of planned analyses, including the handling of subjects whose visits are impacted by the COVID-19 pandemic, will be described in the Statistical Analysis Plan.

10.4.1 Disposition and Demographics

Demographic and baseline characteristics as well as medical history will be summarized using the ITT population, including frequency and percentages for categorical variables and mean, SD, median, minimum, and maximum for continuous variables.

The numbers of subjects in the different analysis populations will be summarized by treatment group, including overall categories.

10.4.2 Efficacy Analyses

All efficacy analyses will be based on the ITT population and will be repeated for the PP population only for the primary and secondary efficacy endpoints as supportive analysis.

10.4.2.1 Primary Endpoint Analyses

The primary estimand of interest is the composite estimand in a patient population offered treatment with tapinarof cream, 1% as compared to vehicle (see Table 6). Interest is focused on the treatment effect measured by the ratio of response rates at Week 8. The primary efficacy endpoint for treatment effectiveness is proportion of subjects who achieve vIGA-AD™ score of clear (0) or almost clear (1) and at least a 2-grade reduction from Baseline at Week 8. Subjects who prematurely discontinue treatment due to an AE or lack of efficacy and subjects who use a prohibited medication with significant impact on efficacy evaluations prior to Week 8 will be considered treatment failure as of the start of the intercurrent event.

Table 6 Primary Estimand Attributes

Estimand Attribute	Description
Treatment	tapinarof cream, 1% compared to vehicle
Population	Intent-to-treat
Variable of interest	Proportion of subjects who achieve vIGA-AD™ score of clear (0) or almost clear (1) and at least a 2-grade reduction from Baseline at Week 8
Intercurrent event handling	Subjects who prematurely discontinue treatment due to an AE or lack of efficacy and subjects who use a prohibited medication with significant impact on efficacy evaluations prior to Week 8 will be considered treatment failure. Investigator assessments will only include data collected at in-person visits.
Summary measure	Ratio of response rates at Week 8

The primary efficacy endpoint will be analyzed using a Cochran–Mantel–Haenszel (CMH) test stratified by vIGA AD™ score at Baseline (vIGA AD™ scores of 3 or 4) and by age group (2-6 years, 7-11 years, 12-17 years, 18 years and above). Handling of missing values is described in Section 10.6.

10.4.2.2 Secondary and Exploratory Efficacy Endpoint Analyses

The secondary efficacy endpoints are as follows:

- Proportion of subjects with $\geq 75\%$ improvement in EASI from Baseline at Week 8
- Mean change in %BSA affected from Baseline at Week 8
- Proportion of subjects with $\geq 90\%$ improvement in EASI from Baseline at Week 8

- Proportion of subjects ≥ 12 years old with a Baseline PP-NRS score ≥ 4 who achieve ≥ 4 -point reduction in the PP-NRS from Baseline at Week 8

Exploratory efficacy endpoints are as follows:

The same methods as discussed for the primary analysis of the primary endpoint will be used to analyze all dichotomized secondary endpoints. The secondary efficacy endpoints will be tested sequentially in the order listed. Testing will stop if non-significance (2-sided $p \geq 0.05$) is observed.

Post-baseline weekly PP-NRS scores will be an average of 7 daily post-baseline PP-NRS scores prior to and including the values assessed on the visit date.

Other efficacy endpoints will be analyzed using CMH test for proportions, and analysis of covariance (ANCOVA) model for continuous variables. CMH tests will be stratified by Baseline vIGA-AD™ score and age group, and ANCOVA models will include vIGA-AD™ score and age group as categorical covariates and Baseline as a continuous covariate.

All endpoints will be summarized descriptively as follows: continuous data will include the mean, SD, minimum, maximum, median, and number of observations; descriptive summary statistics for categorical data will include frequency counts and percentages.

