6. GENERAL ANALYSIS CONSIDERATIONS

The statistical analyses will be reported using summary tables, listings, and figures (TLFs). The International Council for Harmonisation (ICH) numbering convention will be used for all TLFs. Unless otherwise noted, all statistical testing will be 2-sided and will be performed at the 0.05 significance level. Tests will be declared statistically significant if the calculated p-value is <0.05.

Continuous variables will be summarized by presenting the number of observations, means, standard deviations, medians, minimums, and maximums.

Categorical variables will be summarized by presenting counts and percentages of subjects in corresponding categories. All possible categories as defined in the case report form (CRF) should be populated, even if they have zero counts. Percentages for missing values are omitted and do not account for the percent calculation of other categories. Percentages are based on the total category count excluding the missing category if not otherwise mentioned. In certain tables (e.g., TEAEs), the total number of subjects is used as denominator. Footnotes will specify the percent basis in those cases.

All summary tables will be presented by treatment. Baseline summaries will also include a total summary column.

Individual subject data obtained from the eCRFs, external vendors, central clinical laboratory, ECG laboratory, pharmacokinetic (PK) data, and any derived data will be presented by subject in data listings.

The analyses described in this plan are considered a priori, in that they have been defined prior to database lock.

Any analyses performed after breaking the blind (after database lock, for unblinded studies) will be considered post hoc and exploratory. Post hoc analyses will be labeled as such on the output and identified in the CSR.

All analyses and tabulations will be performed using Statistical Analysis System[®] (SAS[®]) software Version 9.4 or higher. Tables, listings, and figures will be presented in rich text format (RTF).

The process for SAS program validation and quality control (QC) for programs and outputs is documented in the Synteract working instruction "SAS programming quality control." Study-specific QC requirements can be found in Appendix B: SAS programming QC requirements.

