10.3 Adjustments for Covariates

The model for the primary, secondary, and exploratory efficacy analyses will include adjustments for the following covariates:

Continuous secondary and exploratory efficacy endpoints (excluding Functional Outcomes and Quality of Life Endpoint) analyzed using ANCOVA models will include baseline vIGA-ADTM score and age group as a categorical covariate and the baseline value as a continuous covariate (see Section 11.2 and Section 11.3).

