11.2 Secondary Efficacy Analyses

The dichotomized secondary endpoints will follow the same composite variable strategy estimand (MI estimand) as the primary analysis of the primary endpoint.

For PP-NRS, if any day of the 7-day period used to compute the average weekly PP-NRS score is on or after the date of the intercurrent event, then the response will be considered a failure for the estimand analysis starting at that visit.

[figure not shown]
Mean change in %BSA will be analyzed with an ANCOVA with factor of treatment and age group*vIGA-ADTM score as a categorical covariate and baseline %BSA as a continuous covariate. The age group*vIGA-ADTM score covariate cohort is as follows:

age group:	vIGA-AD TM score	age group* vIGA-ADTM score cohort
2-6 yrs	3	1
2-6 yrs	4	2
7-11 yrs	3	3
7-11 yrs	4	4
12-17 yrs	3	5
12-17 yrs	4	6
≥18 yrs	3	7
≥18 yrs	4	8

[figure not shown]
The standard MI procedures (Section 10.4) for ANCOVA will be followed. Least squared means of treatment difference (tapinarof – vehicle) along with the 95% CI will be reported. Change from baseline will be assigned to 0 in a manner corresponding to assignment of non-response for the dichotomized secondary endpoints for subjects who discontinue treatment due to an AE or lack of efficacy and subjects who use prohibited medication with significant impact on efficacy evaluations prior to Week 8.

[figure not shown]
The secondary efficacy endpoints will be tested sequentially using the MI estimand analyses. Testing will stop if non-significance (2-sided $p \ge 0.05$) is observed as described in Section 10.7.

[figure not shown]

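### The PP-NRS responder test makes no use of baseline itch, although it is collected and already drives the imputation: a valid analysis, but a missed gain in efficiency

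*Protocol*

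**What the plan says.** Protocol 10.4.2.2 sets the method for EASI75, EASI90 and the PP-NRS responder endpoint: "The same methods as discussed for the primary analysis of the primary endpoint will be used to analyze all dichotomized secondary endpoints". SAP 11.2 carries the estimand over: "The dichotomized secondary endpoints will follow the same composite variable strategy estimand (MI estimand) as the primary analysis of the primary endpoint".

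The primary method, in SAP 11.1, is a CMH analysis stratified by baseline vIGA-AD (3 or 4) and four age groups. The p-value reported for interpretation is not the CMH statistic. It comes from the logit-based common relative risk, log-transformed in each of 100 imputed datasets and pooled in PROC MIANALYZE.

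Continuous endpoints are treated differently. Under SAP 10.3 their ANCOVA models "will include baseline vIGA-ADTM score and age group as a categorical covariate and the baseline value as a continuous covariate". Among the secondary endpoints this applies to one, the change in %BSA.

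SAP 10.4 does put the baseline of each measure into its imputation model, so baseline PP-NRS helps to fill in missing scores. It does not enter the treatment comparison.

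**The concern.** The PP-NRS threshold is an absolute fall in a weekly average. A subject who starts at 4 must reach an average of 0, and a subject who starts at 10 need only reach 6. Baseline itch should therefore predict response, and the present strata are poor substitutes for it. Protocol 5.2 expects about 90% of subjects to share vIGA-AD score 3.

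The endpoint uses only part of the trial, stands last in the fixed sequence and has no stated power. If baseline itch explains much of the variation in response, leaving it out costs precision that the collected data could supply.

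**Working it through.** **1. The plan's own figure.** The only stated power is for the primary endpoint: response "will be 45% for subjects receiving tapinarof compared with 25% for subjects receiving vehicle control, based upon the Phase 2 results", 267 and 133 subjects. "The power is calculated from a Fisher Exact sample size calculation", and the stated result is 97.2%. Full enumeration of the two-sided Fisher test gives 97.6%, and the continuity-corrected formula at 97.2% power returns exactly 133 vehicle subjects. The figure reproduces. It says nothing about PP-NRS.

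**2. Size of the PP-NRS subset.** Protocol 4.1 asks for at least about 15% in each of four age groups.
- Lower bound for age 12 and over: 2 × 15% = 30%, and 0.30 × 400 = 120.
- Upper bound: 100% − 2 × 15% = 70%, and 0.70 × 400 = 280.

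Assuming that 80% of the smaller and 90% of the larger group have baseline of at least 4, the analysed number is 96 to 252. At 45% v 25% (borrowed from the primary endpoint), Fisher power is 44.5% at 64/32 and 86.7% at 168/84.

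**3. Sparse strata.** Within age 12 and over there are 2 × 2 = 4 strata. Assume n = 160 and 10% severe. Then 16 subjects are severe, about 8 per age group, of whom about 8/3 = 2.7 are on vehicle. At 25% response that is 2.7 × 0.25 ≈ 0.7 expected vehicle responders, so cells with zero are common.

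**4. What baseline adds to a model-based test.** Simulation: 45% v 25%, 2:1, baseline roughly normal (7, 1.8) limited to 4–10, 10% severe, complete data, 2,500 runs per cell, and 0.5 added to each cell of a table with a zero cell. The slope is the log-odds of response per baseline point. Entries are power in %.

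| n | slope | planned log-RR | CMH statistic | logistic score test with baseline |
|---|---|---|---|---|
| 96 | 0 | 24.7 | 48.6 | 49.8 |
| 96 | 0.4 | 23.7 | 48.3 | 52.3 |
| 96 | 0.6 | 23.6 | 47.3 | 56.7 |
| 160 | 0 | 50.2 | 70.0 | 70.8 |
| 160 | 0.4 | 49.9 | 70.1 | 73.5 |
| 160 | 0.6 | 48.9 | 68.2 | 76.4 |
| 252 | 0 | 77.2 | 87.2 | 87.8 |
| 252 | 0.4 | 78.0 | 87.8 | 90.8 |
| 252 | 0.6 | 78.0 | 88.5 | 93.6 |

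Against the CMH statistic the score test gains about 1 to 4 points for slopes up to 0.4, and 5 to 9 at 0.6. A slope of 0.6 is steep: vehicle response is 4% at baseline 4 and 62% at baseline 10.

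**5. The proposed test against the planned one.** The score test does not estimate the response ratio. The version that does is a logistic model standardised to the marginal ratio. At n = 160 and an assumed 40% v 24%, the planned log-RR test has 32–34% power and the standardised model with baseline 47–55%, over slopes of 0 to 0.6.

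The lower end can be checked by hand for an unstratified log ratio with 107 and 53 subjects:
- ln(0.40/0.24) = 0.511
- variance = 0.60/(107 × 0.40) + 0.76/(53 × 0.24) = 0.0140 + 0.0597 = 0.0738, so SE = 0.272
- power = Φ(0.511/0.272 − 1.96) = Φ(−0.08) ≈ 47%

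So about 13 to 15 points (32–34% to 47%) come from escaping the sparse strata, and up to 8 (47% to 55%) from baseline itch.

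At 45% v 25% and slopes 0.2–0.6, planned v proposed is about 22% v 37–42% (n = 96), 50% v 65–72% (n = 160) and 77–79% v 86–90% (n = 252). Baseline alone adds about 0 to 6 points there.

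**6. Adding baseline as a stratum.** Splitting baseline at 7 inside the planned log-RR test lowers power in every setting. At n = 160 and slope 0.4 it goes from 49.9% to 40.8%.

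**7. Type I error.** With no effect (n = 160, slope 0.4), the CMH statistic favours tapinarof in 2.3% of trials and the planned log-RR test in 0.7%, against a nominal 2.5%. The proposed test rejects two-sided in 4.0% (n = 96) and 4.9% (n = 160).

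**The case against.** The strongest reply is that nothing here is wrong. The analysis is stratified by both randomisation factors, needs no outcome model and controls type I error. That stands.

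The second reply is that the proposal does not reliably beat an ordinary CMH statistic. At 40% v 24% and slopes of 0 to 0.5, CMH power was 33–35%, 48–50% and 65–67% at n = 100, 150 and 220. The proposed model had 27–33%, 44–49% and 62–70%, and was lower in 11 of 12 settings. This also stands. However, the CMH statistic does not supply the p-value that SAP 11.1 reports, and the pooled log ratio that does supply it is weaker than both.

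Third, these runs assume complete data. Composite failures unrelated to baseline dilute the gain. With an assumed 10% and 20% of such failures (n = 150, slope 0.3), it falls from 2.4 to 1.1 points.

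A reader might infer three stronger things that the documents do not support:
- That baseline is ignored altogether. It is in the imputation model.
- That all responder endpoints lose power and PP-NRS is known to lose most. The smaller subset and absolute threshold make this plausible, but EASI75 and EASI90 are percentage thresholds, their gain was not calculated, and neither document gives the response rates or baseline distributions needed to rank them.
- That the whole gap to the planned test is due to baseline. Much of it is present at slope 0.

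**Conclusion.** The point holds as a missed efficiency gain in a valid analysis, and it is optional. It is not an error, a bias or a contradiction. Baseline PP-NRS itself is worth about 0 to 8 power points, and about 0 to 4 if it is unrelated or moderately related to response. The larger benefit of the proposed model, about 13 to 15 points in the n = 160 example at 40% v 24%, comes from avoiding sparse strata in the pooled log-RR test.

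All these sizes rest on assumed response rates, slopes, subset size and complete data. They also assume about 10% severe subjects. Protocol 5.2 treats that share as a limit and the Synopsis as a minimum, and a larger severe group would make the strata less sparse. Subset size matters more than the covariate: by itself it moves Fisher power from 44.5% to 86.7%.

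**What to change.** In SAP 10.3 and 11.2, for the PP-NRS responder endpoint:
- In each imputed dataset, after the composite failures are applied, fit a logistic model for response with treatment, vIGA-AD stratum, age group and continuous baseline PP-NRS.
- Standardise the fitted probabilities over the analysed subjects to obtain the marginal response ratio, so that the summary measure is unchanged. Pool the log ratio and its standard error in PROC MIANALYZE.
- Do not add baseline as a further stratum to the logit-based relative risk.
- Keep the planned stratified analysis as a sensitivity analysis.
- Record the change in SAP 14, because it departs from the method in Protocol 10.4.2.2, and fix it before unblinding.

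The same model with baseline EASI is optional for EASI75 and EASI90, where the gain was not calculated.

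The cost is SAP wording and one added modelling step; no new data are needed. The drawbacks are a linearity assumption, a method that differs from the primary endpoint's, and little or no gain over an ordinary CMH statistic if baseline itch predicts response only weakly.
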